Study Protocol

**Association Between Body Roundness Index and
Wound Healing Post-Thoracic Surgery: A Prospective
Study**

NCT ID not yet assigned

Unique Protocol ID: TJ-JRB202503009

Data:2025.05.01

Background

The thorax is a vital region of the human body, and the issue of postoperative wound healing following thoracic surgery has long been a subject of clinical concern. Thoracic surgeries—including cardiac surgery, thoracoscopic procedures, and open thoracotomy—are commonly performed for the treatment of cardiopulmonary diseases, tumors, and trauma. Although advancements in surgical techniques and medical equipment have significantly improved surgical success rates, complications such as wound infection, dehiscence, and poor cosmetic outcomes remain relatively common due to the high tension and extensive movement associated with the thoracic region[3]. Poor wound healing in the chest can have a profound impact on patients' psychological well-being, social interactions, and overall quality of life[4]. Excessive tension in soft tissues and skin is considered a key factor contributing to delayed healing and unfavorable scarring. Studies have identified gender, age, and the use of anticoagulants as risk factors for impaired wound healing, while serum lipids may play a protective role. Lipids are critically involved in modulating inflammation, angiogenesis, cellular proliferation, and tissue regeneration, all of which are essential processes in wound healing[5][9].

Obesity has emerged as a growing concern in modern medicine and now poses a serious threat to the health of a large proportion of the population. According to the *Chinese Guidelines for the Diagnosis and Treatment of Obesity*[7], both overweight and obesity exert profound negative effects on multiple organ systems, including the cardiovascular, respiratory, and gastrointestinal systems. Numerous studies have identified excessive obesity as a major risk factor for cardiovascular and cerebrovascular diseases, type 2 diabetes, and chronic kidney disease. In clinical practice, body mass index (BMI) is commonly used to assess obesity[17-19]. However, BMI has several limitations, as it cannot

distinguish between lean body mass and fat mass, nor can it accurately reflect fat distribution throughout the body[7][21]. Recent research by Xiaoqian Zhang and colleagues has shown that the Body Roundness Index (BRI), a novel anthropometric measure, is closely associated with all-cause mortality in the U.S. population. Similarly, the Weight-Adjusted Waist Index (WWI) has gained increasing attention as a new parameter for evaluating body composition, due to its improved accuracy in estimating fat content and its strong correlation with various metabolic risk factors[22].

Recent studies have further confirmed that the Weight-Adjusted Waist Index (WWI), as an indicator of body fat distribution, demonstrates superior predictive value for various conditions, including cardiovascular and cerebrovascular diseases, chronic kidney disease, and urgency urinary incontinence (UUI)[17][23][24]. Despite advances in medical technology and a growing understanding of wound healing among healthcare professionals, postoperative wound complications remain a persistent issue. Although numerous new techniques, materials, and management strategies have been developed to promote wound healing, the incidence of poor wound healing continues to be a significant clinical concern[1][2][9][10].

Objective

By analyzing the associations between factors such as height, smoking history, age, BMI, BRI, waist-to-hip ratio, and lipid profiles with postoperative wound healing, this study aims to elucidate how these variables influence the wound healing process. Understanding these relationships will help identify novel therapeutic targets and support the development of innovative interventions to promote more efficient and effective skin wound healing.

Study Design

The research team conducted discussions and analyses to develop the study protocol, including inclusion and exclusion criteria and the clinical data required for statistical analysis. Clinical and follow-up data of enrolled subjects were collected through the HIS system of Tongji Medical College. Using SPSS version 26.0, subjects were grouped based on whether their wounds achieved secondary healing, and intergroup differences were analyzed to preliminarily identify potential factors associated with impaired wound healing. Subsequently, logistic regression analysis was performed to further determine risk factors influencing wound healing. Multivariate logistic regression analysis was then conducted to identify independent risk factors affecting wound healing. These findings aim to provide clinically feasible intervention strategies to promote more efficient and effective wound healing.

Participant Selection

Inclusion Criteria:

- Patients who underwent surgical treatment in the Department of Thoracic Surgery at Tongji Hospital;
- Complete clinical data and diagnostic test results available;
- Postoperative follow-up conducted regularly in accordance with medical advice, with comprehensive follow-up records;

Exclusion Criteria:

- Without surgery or transferred to other departments;

- Missing basic information;
- Failure to review on time or refusal to follow up;
- Additional surgeries within 30 days of discharge from the hospital;

Sample Size Calculation

A total of 400 patients undergoing thoracic surgery in the Department of Thoracic Surgery at Tongji Hospital, affiliated with Tongji Medical College of Huazhong University of Science and Technology, will be enrolled.

Study Procedure

The research team conducted a thorough literature review to gain a comprehensive understanding of the relevant background before initiating the study design. Inclusion and exclusion criteria, as well as the clinical data required for statistical analysis, were established accordingly. A total of 500 participants are planned for enrollment; subjects not meeting the exclusion criteria will be excluded.

Data collection and follow-up will be conducted using the HIS system of Tongji Hospital. The variables to be collected include gender, age, height (m), weight (kg), waist circumference, abdominal circumference, hip circumference (cm), comorbidities (such as hypertension, coronary heart disease, diabetes), preoperative cholesterol, triglycerides, low-density lipoprotein (g/L), and type of surgery.

Data analysis will be performed using SPSS version 26.0. Initially, independent t-tests will be applied to compare groups based on wound healing status (healed vs. secondary healing) at 30 days postoperatively to identify potential factors associated with impaired wound healing. Variables identified as significant in univariate logistic regression analysis will be entered into a multivariate

logistic regression model. Statistical significance is set at $p < 0.05$. This analysis aims to determine independent risk factors for poor chest wound healing and to propose preventive measures accordingly, culminating in the completion of the study report.

Potential Risks and Mitigation Strategies

This study is observational in nature, with data collected exclusively by inpatient physicians at our hospital. Patient privacy will be strictly protected throughout the data collection process. If any issues related to poor wound healing arise during follow-up, the follow-up personnel will inform patients of appropriate subsequent treatment options. Patients lost to follow-up will be excluded from the study.

Data Collection and Statistical Analysis

Upon admission, patient data including gender, age, height (m), weight (kg), waist circumference, abdominal circumference, hip circumference (cm), comorbidities (such as hypertension, coronary heart disease, diabetes), and preoperative laboratory values including cholesterol, triglycerides, and low-density lipoprotein (g/L) will be collected. Postoperatively, data on the surgical procedure and routine pathological findings will be recorded. Wound healing status will be assessed during a follow-up visit 30 days after surgery. Group comparisons based on wound healing status (healed versus secondary healing) at 30 days will be performed using independent t-tests. Potential factors influencing wound healing will be evaluated using logistic regression analysis. Variables demonstrating statistical significance in univariate analysis will be included in a multivariate logistic regression model. A p -value < 0.05 will be considered statistically significant. This analysis aims to identify independent

risk factors associated with poor chest wound healing and to propose feasible preventive measures accordingly.

References

- [5] Schlager JG, Hartmann D, Wallmichrath J, Ruiz San Jose V, Patzer K, French LE, Kendziora B.

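### Smoking history is named in the Objective as a factor to analyse but is on neither data-collection list, so as listed it can be neither tested nor adjusted for

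*Protocol*

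**What the plan says.** The Objective sets the scope: "By analyzing the associations between factors such as height, smoking history, age, BMI, BRI, waist-to-hip ratio, and lipid profiles with postoperative wound healing", with the aim of explaining how these variables influence healing.

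Two sections then list the data. Study Procedure states "The variables to be collected include gender, age, height (m), weight (kg), waist circumference, abdominal circumference, hip circumference (cm), comorbidities", gives hypertension, coronary heart disease and diabetes as examples of comorbidities, and ends with "preoperative cholesterol, triglycerides, low-density lipoprotein (g/L), and type of surgery". Data Collection and Statistical Analysis repeats this: "Upon admission, patient data including gender, age, height (m), weight (kg), waist circumference, abdominal circumference, hip circumference (cm), comorbidities", followed by the same three lipids and, after the operation, the surgical procedure and routine pathology. Smoking is in neither list.

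Both sections apply the same entry rule to the adjusted model. The later one reads "Variables demonstrating statistical significance in univariate analysis will be included in a multivariate logistic regression model". The stated purpose in Study Procedure is "This analysis aims to determine independent risk factors for poor chest wound healing".

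**The concern.** A factor named for analysis has to be among the data collected. Here the sponsor's own Objective and its own collection lists disagree, and a later analysis plan cannot repair that if the field was never recorded.

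Two things are at stake. The first is the Objective itself: the association of smoking with healing could not be examined. The second is the title question. The study intends to name independent risk factors, and if smoking is related to both BRI and healing, a BRI estimate that omits it carries that confounding.

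The entry rule adds a difficulty. Even if smoking is collected, it reaches the adjusted model only by passing a univariate significance test, which a real effect can fail at this sample size.

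**Working it through.** **Step 1. Objective against the lists.** There is no figure in the protocol to reproduce, so the check is item by item.

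| Factor in the Objective | Obtainable from both lists? |
|---|---|
| Height | Yes, listed |
| Age | Yes, listed |
| BMI | Yes, from weight and height |
| BRI | Yes, from waist and height |
| Waist-to-hip ratio | Yes, from waist and hip |
| Lipid profile | Yes, three lipids listed |
| Smoking history | No: not listed, not derivable |

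Six of seven are covered. Smoking is an exposure, so the comorbidity item, with its three disease examples, does not cover it.

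**Step 2. Illustrative size of the confounding.** The protocol gives no healing-failure rate, smoking prevalence or smoking effect. All inputs here are assumptions: BRI split into halves, binary smoking, smoking odds ratio (OR) 1.5, 2.0 or 2.5, and overall failure of 5%, 10% or 20%.

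The model is logit(p) = a + b·BRI + s·smoking, with a solved to give the overall failure rate. Collapsing over smoking gives the crude BRI OR.

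Example: true BRI OR 1.0, smoking OR 2.0, 10% failure, smokers 50% in the high-BRI half and 30% in the low-BRI half.
- Failure risk is 13.84% in smokers and 7.44% in non-smokers.
- High BRI: 0.5 × 0.1384 + 0.5 × 0.0744 = 0.1064.
- Low BRI: 0.3 × 0.1384 + 0.7 × 0.0744 = 0.0936.
- Crude OR = (0.1064/0.8936) / (0.0936/0.9064) = 1.15, where the truth is 1.0.

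| True BRI OR | Smokers, high v low BRI | Crude OR at smoking OR 1.5 / 2.0 / 2.5 |
|---|---|---|
| 1.0 | 50% v 30% | 1.09 / 1.15 / 1.21 |
| 1.0 | 30% v 50% | 0.92 / 0.87 / 0.83 |
| 1.0 | 45% v 35% | 1.04 / 1.07 / 1.10 |
| 1.0 | 35% v 45% | 0.96 / 0.93 / 0.91 |
| 1.2 | 50% v 30% | 1.30 / 1.38 / 1.44 |
| 1.2 | 30% v 50% | 1.10 / 1.04 / 0.99 |

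The rows for a true OR of 1.2 use 10% failure. In the rows for 1.0, the failure rate changes the results by less than 0.003.

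**Step 3. Would smoking pass the univariate screen if it were collected?** Assume 40% smokers and a two-sided Wald test at 0.05. The sample size is 400 (Sample Size Calculation) or 500 (Study Procedure).

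The standard error of the log OR is √[1/(n₁p₁(1−p₁)) + 1/(n₀p₀(1−p₀))], where 1 denotes smokers and 0 non-smokers. Power is approximately Φ(ln OR/SE − 1.96).

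Example: N = 400, 10% failure, OR 2.0. SE = √[1/(160 × 0.1384 × 0.8616) + 1/(240 × 0.0744 × 0.9256)] = 0.336. Then 0.693/0.336 = 2.06, and Φ(0.10) = 0.54.

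| N | Failure | Probability of passing at OR 1.5 / 2.0 / 2.5 |
|---|---|---|
| 400 | 5% | 0.14 / 0.32 / 0.49 |
| 400 | 10% | 0.23 / 0.54 / 0.77 |
| 400 | 20% | 0.36 / 0.78 / 0.95 |
| 500 | 5% | 0.17 / 0.39 / 0.58 |
| 500 | 10% | 0.27 / 0.64 / 0.85 |
| 500 | 20% | 0.44 / 0.87 / 0.98 |

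At 10% failure (40 to 50 events), a true smoking OR of 2.0 would be left out of the model 36% to 46% of the time.

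**The case against.** The strongest reply is that neither list is exhaustive. Both use open wording and they differ from each other: only the later one includes pathology, and the Study Procedure list omits wound-healing status, which is nevertheless assessed at 30 days. The hospital information system may hold smoking status. This stands as a limit on the claim: the data may still be obtained. It does not remove the mismatch, because both lists go down to individual lipids and hip circumference yet both omit a factor the Objective names.

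A second reply is that no passage links smoking to BRI, so the assumed imbalances are hypothetical and the direction of any bias is unknown. That is correct, and the figures are labelled accordingly.

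A third is that the bias is small beside sampling error. With 400 patients in halves and 10% failure, the SE of the BRI log OR is √[2/(200 × 0.1 × 0.9)] = 0.33. The wider-gap bias is then about 0.25, 0.43 or 0.56 SE, which raises a 5% false-positive rate to about 5.7%, 7.1% or 8.7%. This also stands, and it keeps the point below the most serious grade.

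Finally, the entry rule affects every covariate and is no evidence that smoking is unlisted. That is true; it matters here only because it decides whether adding the field is enough.

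**Conclusion.** The concern holds as an internal inconsistency: smoking history is the only one of seven named factors that the collection lists do not support. That conclusion rests on the protocol's text alone.

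The consequence is conditional. If collection follows the lists, smoking cannot be tested and BRI cannot be adjusted for it. The resulting distortion is modest in most of the assumed scenarios. A BRI OR of about 1.2 is fully created or hidden only at a smoking OR of 2.5 with the 50% v 30% gap. These are crude figures, and adjusting for listed covariates correlated with smoking, such as age and gender, could reduce them.

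This should be corrected before data collection proceeds, because analysts cannot later supply a variable that was not recorded.

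A lesser remark concerns the Background, which states "Studies have identified gender, age, and the use of anticoagulants as risk factors for impaired wound healing". Anticoagulant use is also unlisted, but the protocol does not promise to analyse it, so that is a possible confounding gap and not a contradiction.

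**What to change.** - Add smoking status (never, former, current), recorded at admission, to the lists in Study Procedure and in Data Collection and Statistical Analysis.
- Enter it in the multivariate model for BRI regardless of its univariate p-value, collapsed to ever/never if events are few.
- If it cannot be collected, remove it from the Objective and do not describe the factors found as independent of smoking.
- Optionally, record anticoagulant use for a sensitivity model.

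The cost is one field per patient within data collection already planned, and one or two model degrees of freedom. The protocol does not say whether the hospital system holds smoking status; if it does not, one question at admission is needed.

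### The title asks about BRI alone, but the plan ranks no exposure and puts every factor through one p < 0.05 screen, so BRI may get no adjusted estimate and chance findings can become independent risk factors

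*Protocol*

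**What the plan says.** Only the protocol is available.

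- **Title:** one exposure, "Association Between Body Roundness Index and" wound healing after thoracic surgery.
- **Objective:** "By analyzing the associations between factors such as height, smoking history, age, BMI, BRI, waist-to-hip ratio, and lipid profiles with postoperative wound healing". The list is open-ended and unranked, with BRI fifth of seven.
- **Study Procedure, variables:** "The variables to be collected include gender, age, height (m), weight (kg), waist circumference, abdominal circumference, hip circumference (cm"), then "comorbidities (such as hypertension, coronary heart disease, diabetes), preoperative cholesterol, triglycerides, low-density lipoprotein (g/L), and type of surgery". BMI, BRI and waist-to-hip ratio are not listed and would have to be derived. Smoking history, named in the Objective, is not listed at all.
- **Data Collection and Statistical Analysis, selection rule:** "Variables demonstrating statistical significance in univariate analysis will be included in a multivariate logistic regression model". Study Procedure gives the same rule. Neither makes an exception for any variable.
- **Threshold:** "A p -value < 0.05 will be considered statistically significant". Study Procedure repeats this level. No primary test and no adjustment for the number of factors is stated.
- **Use of the result:** both analysis sections aim to find independent risk factors for poor chest wound healing and to propose preventive measures from them. The Objective also looks to therapeutic targets and new interventions.

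BRI is not mentioned in Study Design, Study Procedure or Data Collection and Statistical Analysis.

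**The concern.** The title and the analysis answer different questions. A study titled for BRI should always yield an adjusted estimate of the BRI association with its confidence interval, whether or not it is significant. The written rule gives BRI a place in the adjusted model only if its univariate p-value is below 0.05. If BRI fails that screen, the title question ends with an unadjusted result. If it passes, the adjusted estimate is reported because the same data had already looked favourable.

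The conclusion drawn is also study-wide. Whichever factors survive are declared independent risk factors and used to support preventive measures. With many factors going through the same rule and none singled out in advance, a per-test threshold of 0.05 does not hold the chance of at least one false declaration near 5%. A lipid or a girth could become the headline result, and a reader could not tell a planned test from the best of many.

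**Working it through.** The protocol states no event rate, effect size, power or study-wide error rate, so there is no plan figure to reproduce. The check follows the written rule when nothing is related to healing.

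**Candidate count**

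- Objective only: height, smoking history, age, BMI, BRI and waist-to-hip ratio (6), plus lipids counted as cholesterol, triglycerides and LDL (3), gives 9.
- Collected plus derived: gender, age, height, weight and three circumferences (7), plus three comorbidities, three lipids and type of surgery (7), gives 14. Adding BMI, BRI and waist-to-hip ratio gives 17, or 18 with smoking history.

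**Ceiling if the tests were independent**, 1 − 0.95^k:

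- k = 7: 30.2%
- k = 9: 37.0%
- k = 17: 58.2%
- k = 18: 60.3%

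The body-size measures are strongly related, so the real figure should be lower.

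**Simulation of the two-step rule, 17 correlated candidates.** Each candidate is fitted alone in a logistic regression. Those with p < 0.05 enter one multivariable model, and a study counts if any p-value there is below 0.05. There were 1,000 null studies per scenario. Assumptions: event rates as shown; weight, BMI, waist, abdominal circumference, BRI and waist-to-hip ratio strongly related (BMI–waist 0.85); cholesterol and LDL about 0.85. Both enrolment figures in the protocol, 400 and 500, were used.

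| n | Event rate | Any univariate p < 0.05 | Any false independent risk factor |
|---|---|---|---|
| 400 | 5% | 40.9% | 29.8% |
| 400 | 10% | 43.3% | 34.7% |
| 400 | 20% | 45.5% | 36.6% |
| 500 | 5% | 41.8% | 33.0% |
| 500 | 10% | 43.3% | 34.6% |
| 500 | 20% | 48.2% | 40.1% |

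The simulation standard error is about √(0.35 × 0.65 / 1000) = 1.5 points. At n = 400 and 10% events, adding smoking gave 36.2%, and lowering the BMI–waist correlation to 0.70 gave 36.3%. With 17 independent candidates the two-step rule gave 59.2%, close to the ceiling.

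**Other assumed correlations, n = 400**

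- 17 candidates: 32–40% in one set of runs; 31/32/34% at event rates of 5/10/15% in another (600 studies each).
- Nine candidates: 25–28% in one set; 26/30/27% at event rates of 5/10/15% in another.

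**BRI alone.** To be declared, BRI must first pass its own univariate test at 0.05. Its false-declaration rate under the null therefore cannot exceed about 5%. Simulated values were 0.4–2.2%.

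The second step is a weak safeguard: in the table it lowers the figure by about 8 to 11 points, because the same data select and then confirm.

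**The case against.** **An unseen SAP may rank the hypotheses and handle multiplicity.** That is fair, and the absence of a multiplicity section is not the point here. What stands is what the protocol itself fixes: a title on one exposure, an Objective that ranks none, and a selection rule with no exception for BRI. An SAP that forced BRI into the model would contradict that rule.

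**The protocol does not say that 17 factors are tested.** This stands. The 14 variables are a collection list. Weight, height and the girths are also inputs to the indices, and nothing says each is tested beside BMI, BRI and waist-to-hip ratio. A reader might infer a fixed count of 17, but the text supports only a range. The list is also open-ended on comorbidities, and routine pathological findings are recorded too.

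**The protocol claims no study-wide 5% error rate.** This also stands. A reader might infer that a stated error rate is breached, or that a BRI finding is itself inflated. Neither is supported: 0.05 is a per-test threshold, and BRI's own false-declaration rate stays within about 5%. The 25–40% is the chance that some factor, not a particular one, is falsely declared.

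**The complete null is extreme.** The Background already cites sex, age and anticoagulant use as risk factors. The figure is therefore a benchmark for the rule, not a forecast for this study.

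**Risk-factor studies are exploratory by nature.** Study Design does call the first group comparison preliminary. The final step carries no such label, and preventive measures are to follow from it.

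**Conclusion.** The concern holds in this form. The title poses a single-exposure question that the stated rule may leave without an adjusted answer. The same rule promotes any survivor to an independent risk factor, with no primary exposure set apart. The loss of an adjusted BRI estimate follows from the wording alone and needs no assumption beyond applying the 0.05 level at the univariate step.

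The chance of at least one false declaration when nothing is related to healing is roughly 25–40% at n = 400. It rests on assumed event rates of 5–20%, assumed correlations, and 9 to 17 candidates, none of which the protocol fixes. The change should be made before analysis; it does not stop the study from proceeding.

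**What to change.** - **Objective:** state that BRI is the single primary exposure and that all other factors are exploratory.
- **Study Procedure and Data Collection and Statistical Analysis:** enter BRI in the multivariable model regardless of its univariate p-value, and test it once at two-sided 0.05.
- **Adjustment set:** name the confounders in advance from the variables already collected. Leave out waist, height and the other girths, because BRI is computed from waist and height (the protocol gives no formula) and the other girths largely duplicate it. Smoking history would have to be added to the collection list before it could be used.
- **Other factors:** report odds ratios with 95% confidence intervals. Do not base independent-risk-factor or preventive-measure conclusions on them alone. False-discovery control is optional.

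With one prespecified primary test, the chance of a false primary finding is 5%. Retitling the work as a multi-factor study would also remove the mismatch, but it would leave the 25–40% in place unless the factors were labelled exploratory or the threshold tightened (Bonferroni: 0.05/9 = 0.0056 or 0.05/17 = 0.0029).

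The cost is wording in the Objective and the two analysis sections, plus the choice of confounders. No extra patients are needed. The downside is that fewer secondary factors can be claimed as significant.

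### Variables enter the multivariable model only by reaching p<0.05 in univariate analysis of the same data, with no prespecified covariates and no limit tied to the number of secondary-healing cases, so the odds ratios of factors that survive the screen are exaggerated and BRI itself can be dropped or diluted

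*Protocol*

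**What the plan says.** The protocol states the entry rule twice. Study Procedure: "Variables identified as significant in univariate logistic regression analysis will be entered into a multivariate" logistic model. Data Collection and Statistical Analysis: "Variables demonstrating statistical significance in univariate analysis will be included in a multivariate logistic regression model". The threshold is given there too: "A p -value < 0.05 will be considered statistically significant". The Study Design sentence, "Multivariate logistic regression analysis was then conducted to identify independent risk factors affecting wound healing", announces the model and its purpose but contains no entry rule.

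The candidates listed in Study Procedure are gender, age, height, weight and three circumferences, followed by "comorbidities (such as hypertension, coronary heart disease, diabetes), preoperative cholesterol, triglycerides, low-density lipoprotein (g/L), and type of surgery". The Objective adds smoking history, BMI, BRI and waist-to-hip ratio.

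On size, Sample Size Calculation gives "A total of 400 patients undergoing thoracic surgery in the Department of Thoracic Surgery at Tongji Hospital", while Study Procedure says "A total of 500 participants are planned for enrollment". Neither figure comes with an expected rate of secondary healing, an effect size or a power. On software: "Data analysis will be performed using SPSS version 26.0". The estimator is not named.

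**The concern.** A variable's p-value and its odds ratio come from the same data. A rule that keeps a variable only when p<0.05 therefore keeps estimates that happened to be large and discards those that happened to be small. The kept estimates are biased away from 1, most strongly when information is scarce. In logistic regression the information comes mainly from the rarer outcome, here the secondary-healing cases, and not from the number of patients. The protocol does not say how many cases it expects and does not restrain the model when they are few.

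The rule also gives the title exposure no protected place. BRI must be computed from the collected body measurements, since it is not itself on the collection list. It competes with several closely related measures and is in the model only if it passes the screen.

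The survivors are to be called independent risk factors, and preventive measures are to be proposed from them. Inflated or missing estimates would feed straight into those proposals.

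**Working it through.** **What cannot be reproduced.** The planned size cannot be re-derived, because the protocol gives no rate, effect or power. Event rates of 5, 10 and 20% are assumptions below, and both stated sizes are used.

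**Candidates.** Collected: gender 1, age 1, height 1, weight 1, circumferences 3, named comorbidities 3, lipids 3, type of surgery 1, in total 14. Smoking, BMI, BRI and waist-to-hip ratio bring this to 18 variables, or 19 parameters if type of surgery has three levels (assumed).

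**Step 1: exaggeration by the univariate screen.** For a factor scaled per SD, SE ≈ 1/√(N·p·(1−p)). Let β = ln 1.3 = 0.262 and a = 1.96 − β/SE (two-sided 0.05 assumed). Among estimates significant in the right direction, the mean log odds ratio is β + SE·φ(a)/(1−Φ(a)).

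| N, rate | Cases | SE | Smallest OR reaching p<0.05, exp(1.96·SE) | φ(a)/(1−Φ(a)) | Mean OR when significant (true 1.3) |
|---|---|---|---|---|---|
| 400, 5% | 20 | 1/√19 = 0.229 | 1.57 | 1.380 | exp(0.262 + 0.229×1.380) = 1.78 |
| 400, 10% | 40 | 1/√36 = 0.167 | 1.39 | 1.059 | exp(0.262 + 0.167×1.059) = 1.55 |
| 400, 20% | 80 | 1/√64 = 0.125 | 1.28 | 0.712 | exp(0.262 + 0.125×0.712) = 1.42 |
| 500, 20% | 100 | 1/√80 = 0.112 | 1.24 | 0.569 | exp(0.262 + 0.112×0.569) = 1.39 |

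**Step 2: the protocol's two-stage rule.** Step 1 is univariate, but the reported odds ratio comes from the multivariable model, so the full rule was simulated (600 to 1,200 runs per setting). Assumptions: 19 correlated candidates; BRI correlated 0.90 with waist, 0.87 with abdominal circumference, 0.82 with BMI and 0.60 with waist-to-hip ratio; true OR 1.5 per SD of BRI, 2.0 for diabetes (12% of patients), 2.0 for one surgery type (12%) and 1.2 per SD of age.

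- Diabetes (true OR 2.0), when it passed the screen with N=400: about 3.9 at 20 cases, 3.1 at 40, and 2.6 to 2.7 at 80. With N=500 and 100 cases: 2.5.
- The same factor in a fixed four-parameter model: log OR 0.60 to 0.70, that is OR 1.8 to 2.0 (fits with a coefficient of 10 or more left out).
- BRI (true log OR 0.405), when it passed the screen, at 20 to 50 cases: mean log OR 0.24 to 0.32, that is OR 1.27 to 1.38 instead of 1.50. In the fixed four-parameter model: 0.39 to 0.41.
- Size of the screened model at 20 to 50 cases: about 3 to 5 variables on average, median 6.7 to 8.8 cases per variable.

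**Step 3: chance that BRI is dropped.** With true OR 1.5 per SD, a = 1.96 − 0.405/SE = 0.19, −0.47 and −1.28 at 5, 10 and 20% (N=400). The chance of passing, 1−Φ(a), is 42, 68 and 90%, so BRI is left out in about 58, 32 and 10% of studies.

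**Step 4: sparse categories.** The chance that a category holding 5% of patients has no case is (1 − 0.05·rate)^N.

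- N=400: 0.9975^400 = 37% at 5%; 0.995^400 = 13.5% at 10%.
- N=500: 29% and 8%.

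**Step 5: does the estimator matter?** Firth's penalised fit after the same screen gave the same diabetes odds ratio as maximum likelihood: 3.92 against 3.92 at 20 cases, and 3.12 against 3.13 at 40. The screen causes the exaggeration.

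**The case against.** Four arguments weigh against a stronger reading, and all of them stand.

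- **The case count is unknown.** A reader might infer that there will be only a few dozen cases. The documents do not say so, and the Background calls wound complications relatively common. At 20% of 500 the exaggeration is modest (1.39 for a true 1.3), and the screened model had fewer than 10 cases per variable in only 7% of simulated studies. The bias shrinks with more cases but does not vanish.
- **Not every odds ratio is inflated.** A reader might infer that BRI's is. In the simulated multivariable model it moved towards 1, because overlapping measures entered with it.
- **Maximum likelihood is not the cause.** The protocol names no estimator, and a penalised fit behind the same screen changes nothing (Step 5).
- **Unusable estimates are not a certainty.** A model with every term forced in would often diverge at low event rates, but the protocol does not fit that model. A single binary factor with no cases fails a Wald screen, and simulated final models then failed in about 0% of runs. Only when type of surgery entered as a multi-level block did 6 to 12% contain an infinite estimate at 20 to 50 cases. Likewise, dividing the cases by all 19 candidate parameters (20/19 = 1.1 at 5%, N=400) does not describe the smaller model that is fitted.

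It can also be said that model details belong in a statistical analysis plan, which may exist. That would answer a silence. Here the protocol chose a selection rule and stated it twice.

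**Conclusion.** The point holds in this form: entry by univariate significance alone, with no prespecified covariates and no link to the number of cases, biases the estimates that the study will report as independent risk factors. Under assumed event rates of 5 to 20% and 400 patients, a true odds ratio of 1.3 per SD averages 1.78 down to 1.42 when selected, and a true diabetes odds ratio of 2.0 averages about 3.9 down to 2.6. A fixed small model stayed near the truth. BRI may be absent or diluted. Empty categories are a risk that depends on the event rate and on how surgery types are grouped.

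The direction of the selection bias does not depend on the assumed rates, but its size does. The diabetes and BRI figures also rest on the assumed effects, prevalences and correlations. This should be changed before analysis. It does not call for a larger study.

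**What to change.** In Study Procedure and in Data Collection and Statistical Analysis, replace the univariate p<0.05 entry rule with the following.

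1. **Prespecified model.** Name a short, ranked covariate list from variables already collected. BRI is always in the model and is the only body-size index in it. If BMI or waist-to-hip ratio is also of interest, put it in BRI's place in a separate, labelled secondary model.
2. **Limit by cases.** Cap the number of parameters by the observed number of secondary-healing cases, dropping from the bottom of the ranked list. As an illustration, the convention of 10 cases per parameter would allow 2, 4 or 8 parameters at 5, 10 or 20% of 400, and 2, 5 or 10 at the same rates of 500.
3. **Sparse categories.** Merge small categories, above all of type of surgery, before looking at outcomes. Alternatively, use a penalised fit if separation occurs. The penalised fit is a safeguard for empty cells only and does not replace item 1.
4. **Reporting.** Give the estimate and confidence interval for every prespecified factor whatever its p-value. Univariate comparisons may stay as description.

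The cost is a change of wording and possibly, for a penalised fit, one run outside the base SPSS menus. The downside is fewer factors in one model and less dramatic odds ratios. No added enrolment or data collection is needed.
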